5 GENERAL CONSIDERATIONS

5.1 General Data Handling

All analyses will be conducted based on SAS 9.4 or higher.

In general, analysis tables will be presented by Visit 3 treatment group using the following groupings of subjects:

- PH94B
- Placebo
- Overall

Data will be presented in by-subject data listings. Subject ID will be four digits consisting of the site ID (first two digits) and subject number (last two digits). Unless otherwise stated, all listings will be sorted by treatment group, subject ID, and assessment date (and time, if available).

Unless stated otherwise, continuous data will be summarized by Visit 3 treatment group based on n, mean, median, standard deviation (SD), minimum value, and maximum value.

Unless stated otherwise, categorical data will be summarized by Visit 3 treatment group using n and percentage based on the number of non-missing values.

The precision level used for descriptive statistics will be based on the following:

- Minimum and Maximum: same number of significant digits as the raw data.
- Mean, Median, Q1, and Q3 (as applicable): one additional decimal place to that reported for Minimum and Maximum
- SD: two additional decimal places than the Minimum and Maximum
- Percentages <100% will be reported to one decimal place and percentages of 100% will be reported with no decimal place.
- P-values will be reported to four decimal places. If the value is below 0.0001 it will be noted as < 0.0001; if the value above 0.9999 it will be noted as > 0.9999.

Unless otherwise noted, statistical inference will be based on a 5% significance level (i.e., 95% confidence intervals will be produced).

5.2 Reference Dates and Definitions

The reference dates for this study are as follows:

- Informed consent date is defined as the eCRF-provided date on which a subject signed the informed consent form.
- Randomization date is defined as the date on which the subject is randomized to study treatment.
- Treatment start date is defined as the date of first dose of IP including dosing of [REDACTED] at Visit 2.

- Treatment end date is defined as the date of last dose of IP.
- The calculation of age will use the informed consent date as its reference date.
- Safety Population data, such as AEs and laboratory assessments, will use the treatment start date as a reference date. In this study, because first dose of PH94B will not occur until Visit 3, AEs will be reported for both prior to Visit 3 IP administration and post.
- Study day will be based on treatment start date as a reference date.

Variable	Definition
Baseline Value	Baseline may refer to the last non-missing value [REDACTED]
Post-Baseline Value	Defined as values collected after IP administration.
Change from Baseline	Defined as: Post-Baseline Value – Baseline Value
Percent Change from Baseline	Defined as: (Value at Post-baseline Visit – Value at Baseline)/Value at Baseline x 100. Note: To compute percent change from baseline, the baseline value cannot be equal to zero.
Temperature (in °C)	= (temperature (in °F) - 32) * 5/9
Height (in cm)	= height (in inches) * 2.54
Weight (in kg)	= weight (in lbs) * 0.4536

5.3 Study Day and Duration Variables

Reference date calculations will generally be defined as the following, assuming non-missing dates:

- date of interest – reference date + 1 when the date of interest \geq reference date;
- otherwise, date of interest – reference date.

If either date is missing, reference date calculations will not be performed.

Study day, based on the treatment start date as the reference, would either have a negative value if collected before dosing or a positive value if collected on or after the day of dosing; there will be no study day zero.

Duration of time is dependent on reference dates and will be calculated in a manner similar to that of the reference date calculation, assuming that dates of interest will strictly follow reference dates (e.g., no negative values). For example, duration on study is defined as the end of study date – treatment start date + 1. Duration of treatment is defined as treatment end date – treatment start date + 1, where treatment end date is the date of last dose of IP.

5.4 Visit Windows

The basis of summarization and analysis will be by visit as recorded in the database. Visit windows will not be applied unless missing dates lead to ambiguity.

5.5 Assigned and Actual Treatment

Once the Investigator deems a subject to be eligible for the study based on inclusion/exclusion criteria, the subject will be randomly assigned at Visit 3 in a blinded manner to either PH94B nasal spray or placebo in a 1:1 ratio.

At the end of the study, assigned treatment will be determined based on randomization number and the unblinded randomization list. Actual treatment will be determined based on batch ID data provided with the final unblinded data.

Intent to Treat (ITT) Population analyses will be conducted based on the randomized (assigned) treatment. Safety Population analyses will be conducted on the basis of the actual treatment received.

5.6 Missing Data

All attempts will be made to ensure completeness of data. Missing safety data will not be imputed and will be presented as collected in the study database. Missing primary efficacy data will be imputed for purpose of analysis, as described below. Missing efficacy data in analyses other than the primary efficacy analysis will not be imputed.

5.6.2 Missing Date Imputation

In cases where adverse event (AE) or medication dates are missing, the following methods will be used to determine flags for treatment-emergent adverse events (TEAEs), prior medications, and concomitant medications.

5.6.2.1 Adverse Event Flags

If the AE start date is completely missing, or if the patient was not treated, no imputation will be conducted. If the AE start date is missing day and month, use the following guidelines to impute dates for purposes of determining treatment-emergent flags:

- If the treatment start date is missing or the AE start year does not fall in the same year as that of the treatment start date or if the AE record contains information to indicate that the event ended before the treatment start date (e.g. the AE end date month and year are earlier than the treatment start date or the full AE end date is known and occurs earlier than the treatment start date), then set the AE start month and day to January 1st.
- Otherwise, set the AE start date to the treatment start date.

If only the AE start day is missing, do the following:

- If the study treatment start date is missing or the AE start month and year does not fall in the same month and year as that of the treatment start date or if the AE contains information to indicate that the event ended before the treatment start date, then set the AE start day to the 1st day of the month of the AE start date.
- Otherwise, set the AE start date to the treatment start date.

AE end dates will not be imputed.

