5.6.2.2 Prior and Concomitant Medication Flags

If medications have missing start or stop dates, appropriate programming logic will be applied to designate the medications as prior or concomitant and, if concomitant, as before or after Visit 3 dosing. If a missing date part leads to uncertainty as to whether a medication is concomitant, the medication will be considered concomitant. If a missing date part leads to uncertainty as to whether a concomitant medication was taken after Visit 3 dosing, the medication will be considered to be taken after Visit 3 dosing.

For example, if the medication start year or end year is after treatment start year, a medication will be considered concomitant even if the month and/or day are missing from the start date or

end date. Likewise, if the medication start occurs in the same year as treatment start, and the medication start month or end month is after the treatment start month, then the medication will be considered concomitant even if the medication start or end day is missing. Similar logic will be applied to other cases of partially missing dates for all designations of prior, concomitant, before Visit 3 dosing, and after Visit 3 dosing.

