6.8 Prior and Concomitant Medication

Prior medications are those which have been identified to have been discontinued prior to the first dose of study medication. Concomitant medications are those which have been identified to have been taken at any point during the study after the first dose of study medication, including medications which started prior to first dose of study drug that are ongoing at first dose. The medications will be coded using B3 WHO Drug Global – Mar 2021.

Partial dates will be imputed according to Section 5.7 for the determination of prior, concomitant, and subsequent medications.

The incidence of prior and concomitant medications will be summarized by Anatomical Therapeutic Chemical (ATC) Level 2 classification and preferred term for all subjects in the Safety Population by treatment group and overall. Concomitant medications will be categorized according to whether they were taken before Visit 3 dosing, during or after Visit 3 dosing, or both. Medications categorized as “Before Visit 3 Dosing” will be those concomitant medications that were taken prior to dosing at Visit 3. Medications categorized as “During or After Visit 3 Dosing” will be those that were taken at any point after dosing at Visit 3. Medications that are ongoing or have an end date that matches the date of Visit 3 dosing will be categorized as “During or After Visit 3 Dosing”. A medication may be counted as both “Before Visit 3 Dosing” and “During or After Visit 3 Dosing” if taken during both time periods.

Finally, all prior and concomitant medication data will be presented in a by-subject listing. The listing will include ATC Level 2 classification, preferred term, and verbatim term.

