8.1 Adverse Events

An AE is any symptom, sign, illness, or experience that develops or worsens in intensity during the course of the study. Any newly developed illnesses or injuries should be regarded as adverse events. AEs will be assessed for severity, relationship to study drug, and seriousness. Further details about AE determination and categorization can be found in the study protocol.

Serious adverse events (SAEs) will be recorded starting at Visit 1 after signing informed consent. AEs will be recorded from the time of first IP administration through end of study. A TEAE is defined as any AE occurring on or after start of IP. All summaries of AEs will be based on TEAEs. All AEs recorded on the eCRF, whether treatment-emergent or not, will be presented in a data listing. Non-TEAEs will be flagged in the listings.

All AE data will be reported for two time periods: prior to Visit 3 dosing, and during or after Visit 3 dosing. This is due to the fact that all subjects receive [REDACTED] at Visit 2 and then receive randomized treatment [REDACTED] at Visit 3. AEs will be assigned to a time period based on AE start date. An AE that starts on the day of Visit 3 dosing will be assigned as “during or after Visit 3 dosing”. From Screening until IP administration at Visit 2, any clinically significant abnormality should be recorded as a preexisting condition in the medical history, not as an AE.

All AE terms will be coded by using MedDRA, version 24.0 – Mar 2021.

Missing and partially missing start and/or end dates will be imputed for the purpose of determining treatment-emergent flags and AE categorization, according to Section 5.7.

The incidence of TEAEs will be summarized by maximum severity and strongest relationship to IP. When calculating the incidence of TEAEs, each TEAE will be counted only once for a given subject within a MedDRA category (i.e., overall, SOC, or PT). When TEAEs are summarized within levels of another TEAE assessment (i.e., severity or relationship), TEAEs will be counted once per subject at the worst level of the assessment (i.e., greatest severity or relationship to IP). Any missing severity assessments will be assumed to be severe and missing relationship assessments will be assumed to be related.

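### The SAP has no clear rule for placing adverse events with a partial onset date before or after Visit 3 dosing; its only date rule, if used for that split, errs in one direction

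*SAP*

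**What the plan says.** **The split.** SAP 8.1 reports all AE data for two periods, before Visit 3 dosing and during or after it, and states: "AEs will be assigned to a time period based on AE start date". An AE starting on the Visit 3 dosing day belongs to the later period. SAP 4.3 gives the aim, which is to see more clearly which events followed which exposure.

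**The date rule.** SAP 5.6.2 introduces its date methods by saying that "the following methods will be used to determine flags for treatment-emergent adverse events (TEAEs), prior medications, and concomitant medications". For AEs, 5.6.2.1 works as follows:
- If the known parts of the onset date do not match the treatment start date, or the event is known to have ended before it, the missing parts become the 1st of the month or 1 January.
- In the remaining cases: "Otherwise, set the AE start date to the treatment start date".
- "If the AE start date is completely missing, or if the patient was not treated, no imputation will be conducted".
- "AE end dates will not be imputed".

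SAP 5.2 defines the treatment start date as the first dose of investigational product, at Visit 2. SAP 2 shows that this dose is placebo. No branch of 5.6.2.1 refers to Visit 3.

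**The link between the two.** SAP 8.1 says missing and partial start and/or end dates are imputed to set treatment-emergent flags and to categorise AEs, and cites Section 5.7. SAP 6.8 has the same reference for medications: "Partial dates will be imputed according to Section 5.7 for the determination of prior, concomitant, and subsequent medications". Section 5.7 is Multiplicity and contains no date rule. SAP 5.6, for its part, says: "Missing safety data will not be imputed and will be presented as collected in the study database".

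**Medications.** SAP 5.6.2.2 does provide for Visit 3. If a missing date part leaves it uncertain whether a concomitant medication was taken after Visit 3 dosing, "the medication will be considered to be taken after Visit 3 dosing".

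**The concern.** PH94B is first given at Visit 3, so the period split is the SAP's own means of separating placebo lead-in events from events on randomised treatment. A programmer meeting an AE with a partial onset date has two choices, and neither serves the aim in 4.3.

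- Use the 5.6.2.1 date for the split. That date is built to protect the treatment-emergent flag and sits as early as the known parts allow after Visit 2, so events that began after Visit 3 tend to be labelled lead-in.
- Leave the date as collected. Then no rule places the event unless the known month already does so.

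At stake is a descriptive count of events in the randomised-treatment period. On the first choice, that count could be too low in both arms.

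**Working it through.** The documents give no figure on this point, so there is none to reproduce.

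**Inputs.** Anchor: the Visit 2 dose (SAP 5.2). Period boundary: the Visit 3 dosing day (SAP 8.1). Visit spacing: 7 days, window 5 to 9 (Protocol 5.2.2 and 5.2.3). Assumptions not in the documents: Visit 2 dates uniform over 365 days, onset equally likely on each of the 7 days starting with Visit 3, and no informative end date.

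**1. Direction (no distributional assumption needed).** For an onset on or after Visit 2, the imputed date is Visit 2, the 1st of the onset month, or 1 January of the onset year. None is later than the true onset, so a lead-in AE cannot move forward. None is earlier than Visit 2 either, because the 1st-of-month and 1 January branches apply only when the onset month or year is later than that of Visit 2. No treatment-emergent flag is lost. Enumeration agrees: 0 of 2,555 lead-in combinations move forward, and 0 of 6,205 flags are lost.

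**2. Examples, 7-day spacing, day of onset missing.**

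| Visit 2 | Visit 3 | Known onset | Imputed | Period |
|---|---|---|---|---|
| 5 Oct | 12 Oct | Oct | 5 Oct | lead-in |
| 28 Oct | 4 Nov | Nov | 1 Nov | lead-in |
| 20 Oct | 27 Oct | Nov | 1 Nov | after Visit 3 (correct) |

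In the first two rows the true onset may lie on either side of Visit 3, but the rule always gives lead-in.

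**3. Share misplaced if imputed dates feed the split.** Take a true onset k days after Visit 3. With only the day missing, it is placed correctly only if a 1st of the month falls among the k + 1 days from Visit 3 to onset. The misplaced share is therefore 1 − 12(k + 1)/365.
- k = 0: 1 − 12/365 = 96.7%.
- Mean over k = 0 to 6, where k + 1 averages 4: 1 − 48/365 = 86.8% (2,219 of 365 × 7 = 2,555).
- Mean over k = 0 to 9, where k + 1 averages 5.5: 1 − 66/365 = 81.9%.
- Day and month both missing, k = 0 to 6: 1 − 4/365 = 98.9% (2,527 of 2,555).

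These are shares of calendar combinations, not counts of AEs.

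**4. If imputed dates do not feed the split.** With the day missing, the known month settles the period when it lies wholly on or after Visit 3. That is 48/365 = 13.2% (336 of 2,555) of post-Visit 3 onsets. The other 86.8% have no rule.

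**5. The medication-style convention applied to AEs.** It places every post-Visit 3 AE correctly. A lead-in AE that began j days before Visit 3 moves forward unless a 1st of the month falls in those j days, so the share moved is 1 − 12j/365. Averages before any end date or recording date is used:
- 7-day spacing (mean j = 4): 86.8%.
- 5-day spacing (mean j = 3): 1 − 36/365 = 90.1%.
- 9-day spacing (mean j = 5): 1 − 60/365 = 83.6%.

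**6. Effect on the comparison of arms.** Among day-missing AEs, let a and b be the expected post-Visit 3 counts on PH94B and placebo, and c the expected lead-in count per arm. The lead-in precedes 1:1 randomisation at Visit 3, so c is the same in both arms.
- 5.6.2.1 dates used for the split: 0.132a against 0.132b. The ratio is kept and the difference shrinks to 13.2% of its value.
- Medication-style rule: a + 0.868c against b + 0.868c. The difference is kept and the ratio moves toward 1.

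**The case against.** A reader might infer that the SAP sends PH94B-period events into the placebo lead-in and so under-reports harm. The documents do not support that. SAP 5.6.2 and 5.6.2.1 name only treatment-emergent flags, and 5.6 says missing safety data are not imputed. SAP 8.1 also uses the idea of categorisation in pointing to the protocol, directly after severity, relationship and seriousness. That the imputed dates feed the period split is an inference. It is a plausible one: a date decides none of those three attributes, and the period is the only other AE category in 8.1 that a date does decide. But it is not stated.

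The affected records are also likely to be very few. AEs are sought at every contact (Protocol 6.3.1), visits are about a week apart, and an event on the Visit 3 day happens largely in front of staff. The SAP is to be read with the case report form, which is not available here and may capture timing in another way. The uniform-date assumptions have no source in the documents.

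Finally, the remedy reverses the error and does not remove it, as step 5 shows. Calling it conservative holds for absolute counts in the PH94B period, but not for the ratio between arms.

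All of this stands as a limit on size and certainty. It does not supply the missing rule. On either reading the SAP gives AEs no placement that serves the aim in 4.3, while the adjacent subsection gives medications one.

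**Conclusion.** The point holds as a minor one. The SAP splits AEs at Visit 3 dosing but has no date rule written for that split. If the 5.6.2.1 dates are used, misplacement runs one way only, from after Visit 3 to the lead-in. If they are not, AEs with a partial onset date have no period rule unless the known month settles it. The direction follows from the text. The 86.8% for a missing day rests on uniform visit and onset dates and describes calendar combinations, since the number of partial dates is not given.

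Nothing beyond a descriptive period label on probably very few records is affected. Treatment-emergent flags, treatment columns and listings do not change, and SAP 8 plans no formal safety test. The wrong Section 5.7 references and the conflict between 8.1 and 5.6.2.1 on end dates are clerical, but they are errors on any reading.

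**What to change.** 1. State that the 5.6.2.1 dates serve the treatment-emergent flag only.
2. Add to SAP 8.1 a period rule parallel to 5.6.2.2. A treatment-emergent AE with a partial start date, in a subject dosed at Visit 3, goes to the period during or after Visit 3 dosing if the known date parts allow it. The exception is where a known end date before Visit 3 dosing, or (if available as data) a record made before Visit 3 dosing, rules this out. Otherwise it goes to the earlier period.
3. Report by arm how many AEs were placed by this rule.
4. Housekeeping: change the Section 5.7 references in 6.8 and 8.1 to 5.6.2, and reconcile 8.1 with 5.6.2.1 on whether AE end dates are imputed.

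The cost is a few lines of SAP text and one extra count in the output. The downside is that some true lead-in AEs will be counted after Visit 3, about equally in both arms. This raises absolute counts and pulls the ratio between arms toward 1, but leaves the expected difference in counts unbiased. The choice is one of convention. It keeps every post-Visit 3 event in its period and matches the SAP's handling of medications and its worst-case handling of missing severity and relationship.

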5.6.2.2 Prior and Concomitant Medication Flags

If medications have missing start or stop dates, appropriate programming logic will be applied to designate the medications as prior or concomitant and, if concomitant, as before or after Visit 3 dosing. If a missing date part leads to uncertainty as to whether a medication is concomitant, the medication will be considered concomitant. If a missing date part leads to uncertainty as to whether a concomitant medication was taken after Visit 3 dosing, the medication will be considered to be taken after Visit 3 dosing.

For example, if the medication start year or end year is after treatment start year, a medication will be considered concomitant even if the month and/or day are missing from the start date or

end date. Likewise, if the medication start occurs in the same year as treatment start, and the medication start month or end month is after the treatment start month, then the medication will be considered concomitant even if the medication start or end day is missing. Similar logic will be applied to other cases of partially missing dates for all designations of prior, concomitant, before Visit 3 dosing, and after Visit 3 dosing.

5.7 Multiplicity

Testing of the secondary endpoint will proceed once the primary endpoint achieves statistical significance. In this way, Type I error is well controlled.

6 STUDY SUBJECT DATA

6.1 Subject Disposition

All subjects who provide informed consent will be accounted for in this study. The number of subjects randomized, completed, and discontinued from the study, as well as reasons for discontinuation, will be summarized by treatment group and overall. Additionally, the number of subjects in each analysis population will be displayed. Data will also be presented in a by-subject listing.

6.2 Protocol Deviations

Protocol deviations will be identified via the eCRFs and classified as major or minor deviations before the database is locked. Protocol deviations will be summarized for the All Subjects Population by treatment group (including “not randomized”) and overall. Data will also be presented in a by-subject listing.

